PD; Pharmacokinetic = PK; Procollagen type 1 N-propeptide = P1NP; Prothrombin Time/ Prothrombin Time = PT/INR; Red Blood Cell Count = RBC; Thromboplastin Time = PTT; Serious Adverse Event = SAE; QD = Once daily; Total Bilirubin = Tbili; Triglycerides = TGL; White Blood Count = WBC; Women Of Child Bearing Potential = WOCBP

- If participant discontinues from the study early (ET) or withdraws from taking CLTX-305 (encaleret) (EoT), before completing Period 3 per protocol, participant will be asked to return to the NIH CC as soon as possible for the ET/EoT visit assessments and return the unused CLTX-305 (encaleret). Participant should revert to their outpatient regimen of oral calcium and active vitamin D. Participants will go through FU activities as stated in table and footnote 2, and then will have a safety FU call 30 day ± 7 days.
- Participants who withdraw from taking CLTX-305 (encaleret) (EoT) before completing Period 3 per protocol or who elect not to continue into the LTE will obtain the following outpatient laboratory assessments after the last dose of CLTX-305 (encaleret) and after re-starting their prior regimen of oral calcium and active vitamin D: blood Cr, Ca, Alb, Mg, PO4. Follow-up (FU) call should occur within 3-5 days to review the lab results and receive guidance on clinical management of their ADH1 as they transition to their prior clinical care providers.
- Unscheduled visits: For laboratory evaluation following dose adjustment or assessment or follow-up of an AE, in which clinically indicated procedures will be performed.
- Document current CLTX-305 (encaleret) dose and calcium dosing regimen, any modifications, and reason for modifications.
- Outpatient laboratory testing: Blood samples for clinical laboratory panels (Na, Cl, bicarbonate, K, BUN, Cr and including Alb, Ca, Mg, PO4, iPTH, CTX and P1NP).
- 6 Height measured only at ET visit.
- Vital signs include supine or sitting blood pressure (BP) by automated cuff, heart rate (HR), and respiratory rate.
- Focused Physical exams: weight measurement at all visits.
- Safety Labs collected at the NIH CC visits—Chemistry (Na, K, Cl, bicarbonate, Glu, BUN, Cr, Alb, total protein, Ca, Mg, PO4, 25-OH Vitamin D, Cholesterol, TG, AST, ALT, Tbili, Alk phos, LDH, amylase, lipase, uric acid), Hematology (RBC, Hgb, Hct, RBC indices, WBC, diff), Coagulation (PT/PTT/INR).
- 10 CLTX-305 (encaleret) administered and recorded during the NIH CC visit/in-house PK/PD collection days.

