# 6.1.8 Dose Modifications

See above for general principles of dosing and titration limitations based on toxicity or hypercalcemia. See Section 8.2 for details of the dosing guidance algorithm for each Period.

Dose modifications should be made according to the protocol-specified guidance/algorithm described in Section 8.2 based on cCa thresholds of > 10-10.5 mg/dL in Period 1 and > 10 mg/dL in Period 2. Similarly, titration in outpatient Period 3 and the LTE will be based primarily on periodic assessment of cCa and where cCa > 10 mg/dL would also require dose modification.

For participants who develop clinical laboratory abnormalities unrelated to the dosing algorithm parameters (e.g., corrected calcium) indicating that further conduct of per protocol clinical assessments/procedures may put the participant at risk may have their CLTX-305 (encaleret) dosing interrupted at the discretion of the principal investigator and should be captured as adverse events. Because of the intensive sampling required during the conduct of the in-hospital assessments, procedures related to the collection of blood in terms of sampling technique or frequency of sampling and/or blood volume may have their scheduled dosing interrupted so as to allow the patient to recover and continue the study treatment at a later date (re-initiation). The time interval separating the day of the interrupted dose and the day to re-initiate dosing will be less than or equal to 56 days. The participant with an interrupted dose may be re-initiated at the next protocol-specified dose level of CLTX-305 (encaleret) at the discretion of the principal investigator. A participant with a dose interruption shall continue to meet eligibility criteria for the study.

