### Addition of Oral Calcium Supplements and/or Calcitriol

Since all participants will be attempting to consume at least 1000 mg dietary calcium per day throughout the trial, additional supplemental oral calcium in the range of 1,000–2,000 mg additional supplement may be given as required with close follow-up of cCa. Transient requirements for calcium supplementation and/or 1-2 doses of calcitriol (at doses based on each participant's prior known sensitivity and dosing of outpatient calcitriol, if known, e.g., likely in the range of 0.5-2 mcg) resulting in stabilized calcium levels, need not interfere with per protocol dose escalation, particularly if required on Days 1 and 2 before CLTX-305 (encaleret) effective doses may have been achieved. More severe or prolonged hypocalcemia unresponsive to oral supplementation may require early termination from the study period at the judgement of the investigator. If calcium levels are not stable and if evidence of clinically significant hypocalcemia precludes further dosing in the study period, CLTX-305 (encaleret) dosing will be stopped and participants may be re-started on their prior outpatient regimen of oral calcium and calcitriol and discharged when stable, with close follow-up. Such participants may be eligible to return for either a repeat of the study period or to the next per protocol study period, at the discretion of the investigator and the Sponsor.

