For Period 1 Day 1 to Day 4 and Period 2 Day 1 to Day 4 and time-interval 17-24 hours, the 15 minutes pre-dose results from the following visit will be used (for example 15 minutes pre-dose Day 2 will be used to derive the 17-24 hours fractional excretion).

10.4 Study Day 1

For Period 1 assessments:

The day of the first dose of study drug in Period 1 is referred to as "Study Day 1".

For Period 2, Period 3 and LTE assessments:

The day of the first dose of study drug in Period 2 is referred to as "Study Day 1".

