10.12 Analysis Visit Window

For initial screening the target day is -60 to -2 days before baseline. The visit will be mapped to screening if study day is -61 to -1 days. For Periods 1 and 2 once subjects are admitted to the inpatient facility, analysis will be performed for the day/time as scheduled.

For Period 3 and LTE, since the actual visit for a subject may not exactly coincide with the scheduled visit date, the actual visit date will be mapped to the study analysis visit as follows.

Analysis Visit	Target Day	Study Day	Interval (days)
Week 1	13	13	7 - 16
Week 2	20	20	17 - 23
Week 3	27	27	24 - 30
Week 4	34	34	31 - 41
Week 6	48	48	42 - 55
Week 8 (NIH visit)	62	62	56 - 76
Week 12	90	90	77 - 104
Week 16 (NIH visit)	118	118	105 - 132
Week 20	146	146	133 - 160
Week 24 (NIH visit)	174	174	161 - 188
Follow-up* (2-3 days post last dose)	No analysis visit window applies		
Follow-up* (7 days post last dose)	No analysis visit window applies		dow applies
Follow-up* (30 days post last dose) No analysis visit window applies		dow applies	

Table 3: Period 3 Analysis Visit Windows

* Follow-up visits are only performed if the subject does not continue in the LTE.

For the LTE, subjects will continue CLTX-305 (encaleret) per the dosing regimen established in the maintenance phase of Period 3. Telephone contacts along with outpatient laboratory assessments will be performed every 6 months starting at Month 3 with NIH inpatient visits occurring every 6 months starting at Month 6. The actual visit date will be mapped to the study analysis visit as follows.

Table 4: LTE Analysis Visit Windows

Analysis Visit	Target Day	Study Day	Interval (days)
Month 3	264	264	189 - 309
Month 6	354	354	310 - 399
Month 9	444	444	400 - 489
Month 12	534	534	490 - 579
Month 15	624	624	580 - 669
Month 18	714	714	670 - 759
Month 21	804	804	760 - 849
Month 24	894	894	850 - 939
Follow-up (2-3 days post last dose)	No analysis visit window applies		
Follow-up (7 days post last dose)	No analysis visit window applies		
Follow-up (30 days post last dose)	Ν	lo analysis visit win	dow applies

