For assessments where more than one actual visit falls within the same defined window and it is not an inpatient NIH visit (Weeks 8, 16 and 24, Months 6, 12, 18 and 24), the visit closest to the target day with non-missing data will be considered for analysis. If two actual visit dates are at the same distance from the target day, the latest visit with non-missing data will be considered for analysis. If the scheduled visit is an inpatient NIH visit, the NIH inpatient visit will be considered for analysis.

All summaries and analyses will utilize analysis days/visits, where appropriate. Data listings will present actual day/visit names as recorded in the clinical database.

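### At outpatient visits, SAP 10.12 lets an unscheduled lab, drawn after a dose change or for an adverse event, replace the scheduled value because it lies nearer the target day

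*SAP*

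**What the plan says.** For Period 3 and the LTE, SAP 10.12 assigns records by date: "the actual visit date will be mapped to the study analysis visit as follows". Tables 3 and 4 give a target day and an interval for each visit. Where two or more records for an assessment share an interval and the visit is not an NIH inpatient visit, "the visit closest to the target day with non-missing data will be considered for analysis"; if two are equally distant, the later one is used.

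NIH visits (Weeks 8, 16 and 24; Months 6, 12, 18 and 24) have their own rule: "If the scheduled visit is an inpatient NIH visit, the NIH inpatient visit will be considered for analysis".

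The protocol explains why off-schedule labs exist. Table C footnote 3 reads: "Unscheduled visits: For laboratory evaluation following dose adjustment or assessment or follow-up of an AE". Table D footnote 3 says the same for the LTE. Protocol 6.1.5 also foresees titration at unscheduled as well as scheduled telephone contacts.

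The labelled values are used in SAP 13.7.1 and 13.7.2 (absolute values and changes by visit) and in SAP 13.7.4 (Period 3 paired t-tests at each visit for cCa, iPTH, phosphorus, magnesium and total calcium excretion).

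**The concern.** A scheduled lab is drawn because the calendar says so. An unscheduled lab is drawn because a dose was just changed or something happened to the participant. A rule that ranks records only by distance from a target day treats the two as interchangeable. Participants whose calcium is unstable are the ones with extra records, so they are the ones whose scheduled value can be replaced.

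At stake is the meaning of the outpatient rows in the Period 3 and LTE tables, and of the Period 3 t-tests at those visits. The rows would mix planned measurements with measurements triggered by the outcome. Most of the exposed weeks lie in the titration phase of about 12 weeks, when doses change most. Because the choice is made per assessment, one participant's analytes in one visit row may also come from different dates and doses.

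**Working it through.** **1. Reproducing the SAP's windows.** Target day = 6 + 7 × week gives 13, 20, 27, 34, 48, 62, 90, 118, 146 and 174, as in Table 3. Target day = 174 + 30 × month gives 264 to 894, as in Table 4. The Week 1 to Week 20 upper limits are the midpoints between neighbouring targets, rounded down.

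**2. When the nearest-to-target rule comes into play.** Tables C and D allow ±2 days at Weeks 1-4, ±5 days from Week 6 on, and ±7 days at the LTE outpatient months. Centred on the SAP targets, every Period 3 scheduled visit made within its allowance stays in its own window: Week 1 on days 11-15 (window 7-16), Week 4 on 32-36 (31-41), Week 6 on 43-53 (42-55), Week 20 on 141-151 (133-160). For visits kept on schedule, two records in one window therefore means that one is unscheduled. That is the case the rule has to decide.

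**3. How often the unscheduled record is used.** Assumptions: exactly one unscheduled lab containing the analyte falls in the window, uniformly over its L days; the scheduled visit is uniform over its allowance of ±A days around the target.

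- Scheduled visit d days early: displaced by a draw at offsets −(d−1) to +d, which is 2d days, because a tie goes to the later record.
- Scheduled visit d days late: displaced at offsets −(d−1) to +(d−1), which is 2d−1 days.
- Scheduled visit on target: cannot be displaced.

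Summing over d = 1 to A gives A(A+1) + A² = A(2A+1) displacing pairs out of (2A+1) × L, so the share is A/L.

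| Visit | A | L (days) | Displacing / all pairs | Share |
|---|---|---|---|---|
| Week 1 | 2 | 10 | 10/50 | 20.0% |
| Weeks 2, 3 | 2 | 7 | 10/35 | 28.6% |
| Week 4 | 2 | 11 | 10/55 | 18.2% |
| Week 6 | 5 | 14 | 55/154 | 35.7% |
| Weeks 12, 20 | 5 | 28 | 55/308 | 17.9% |
| Month 3 | 7 | 121 | 105/1815 | 5.8% |
| Months 9, 15, 21 | 7 | 90 | 105/1350 | 7.8% |

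**4. Scale of one replacement.** SAP 8.1 plans about 16 participants. As an illustration only, if the two records differ by 1 mg/dL in cCa, one replacement moves the visit mean by 1/16 = 0.06 mg/dL.

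**The case against.** The rule is explicit and reproducible, and listings keep the actual visit names, so a substitution can be traced. Only interim outpatient rows are exposed, the t-tests are labelled post hoc, and Protocol 9.1 plans description without hypothesis testing. Scheduled labs in a titration study also follow and prompt dose changes. Outpatient 24-hour urine during Period 3 dosing is scheduled only at Week 20, so urinary calcium is barely touched. The direction of any bias is not shown, and the percentages are not rates.

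Most of this stands, and it limits the point. It does not answer it. A reproducible rule can still select on the outcome, and traceability in listings does not correct the summary tables. The SAP does set unscheduled results aside elsewhere (the PK concentration listing, 13.8.2), but 10.12 has no such statement.

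A reader might infer two stronger things.

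- **That an unscheduled lab can enter the primary Week 24 result.** The NIH-visit sentence in 10.12 prevents this whenever the NIH visit lies in its window.
- **That a restarted Period 2 would put Week 20 or Week 16 data under Week 24.** SAP 10.4 counts days from the first Period 2 dose, and Protocol 6.1.8 allows re-initiation up to 56 days after an interruption. With that anchor fixed, a delay of 15-42 days moves Week 20 to days 161-188, and one of 43-56 days moves Week 16 to days 161-174, both inside the Week 24 window. The documents do not support this as a defect. SAP 10.13 (Period 2 special considerations) and 10.15 (other subject data considerations) are listed in the contents, but their text is not in the copy available, and either may reset Study Day 1. The NIH-visit sentence can also be read as keeping the scheduled Week 24 visit whatever its day. Nothing legible shows that such a restart occurred.

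**Conclusion.** The point holds for outpatient visits only: Weeks 1-4, 6, 12 and 20, and LTE Months 3, 9, 15 and 21. As written, SAP 10.12 allows a lab triggered by a dose change or an adverse event to replace the scheduled value in the by-visit laboratory summaries and, in Period 3, in the paired t-tests at those weeks.

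Given one unscheduled lab in the window, the chance of replacement is highest at Week 6 and lowest in the LTE, as tabulated above. Those shares rest on the two uniformity assumptions. The overall rate is unknown because the frequency of unscheduled labs is not given. The direction of the effect is also unknown: a lab prompted by low calcium and a lab after a dose increase could pull a visit mean opposite ways.

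This is a moderate weakness in the outpatient analyses. It does not challenge the primary Week 24 result when the NIH visit lies in its window.

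**What to change.** In SAP 10.12, state that a scheduled visit with non-missing data in the window is the record analysed, and that an unscheduled record is eligible only when the scheduled value is missing. The nearest-to-target rule and its tie-break then apply only among the eligible records. With that wording, the number of days on which an unscheduled draw can displace an available scheduled value falls to zero.

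The cost is the SAP wording and a change to one derivation program. Visit names are already recorded in the clinical database, so no new data are needed.

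Separately, and only as a confirmation, the sponsor could point to where 10.4, 10.13 or 10.15 sets Study Day 1 for an interrupted or repeated Period 2.

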10.14 LTE Data

For administrative purposes, LTE data for participants may be housed in the eCRF for CLTX-305-201 and in the eCRF for CLTX-305-302/CALIBRATE. When the NIH site is activated in CLTX-305-302/CALIBRATE, the database for CLTX-305-201 will be cleaned and closed. LTE participants will be able to consent to the LTE portion of the CLTX-305-302/CALIBRATE study for the purpose of data entry to support the LTE summary of the CLTX-305-201 CSR. LTE data captured in the database of CLTX-305-201 and CLTX-305-302/CALIBRATE for these participants will be summarized in the CSR for CLTX-305-201. The CSR for CLTX-305-302/CALIBRATE will not include data from the subjects originating from CLTX-305-201.

A central lab will be used in CLTX-305-302/CALIBRATE. The lab data of the participants of CLTX-305-201 collected in the central lab and the lab data collected in CLTX-305-201 will be analyzed in the same outputs

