10.0 Conventions and Derivations

10.1 Baseline

Baseline is defined as the last non-missing value before the first dose of study drug is administered to each subject. For subjects that are enrolled in either Period 1 and/or Period 2, baseline is the last non-missing value before the first dose of study drug in that period. For cohort 1 subjects, if there are no assessment performed prior to the first dose of Period 2, the baseline for Period 1 will be used as the baseline for Period 2. For Period 3 and LTE baseline is the same as the baseline for Period 2.

Laboratory parameters:

For the timed-intervals urine parameters, the baseline will be defined as follows:

• For the parameters collected as time-intervals (i.e. the results from samples collected at 15 minutes pre-dose, 0 to 4 hours, 4 to 8 hours, 8 to 13 hours, 13 to 17 hours and 17 to 24 hours), the baseline for Period 1 will be the 15 minutes pre-dose urine sample collected at Period 1 Day 1; the baseline for Period 2, Period 3 and LTE will be 15 minutes pre-dose urine sample collected at Period 2 Day 1.

• For the parameters collected on 0-24 hours, screening assessments will be considered as baseline (regardless of the laboratory analyzing the samples, local laboratories or NIH laboratory).

For chemistry parameters (serial sampling), the 15 minutes pre-dose samples on Day 1 from Period 1 will be the baseline for Period 1 and the 15 minutes pre-dose samples on Day 1 of Period 2 will be the baseline for Period 2. Screening values will be used for the count and percentage of subjects with a >50% decrease in 24-hr urine calcium excretion.

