13.6.3 Laboratory Data

Safety Laboratory data (hematology and chemistry) will be presented using SI units and tabulated by dose, day and time-point (where applicable) for Period 1; by day and time-point (where applicable) for Period 2, and by analysis visit and time-point (where applicable) for Period 3 and by analysis visit for LTE.

Absolute values and change from baseline will be summarized. Creatine Kinase and Potassium will be summarized by time-points. The mean \pm SD of creatine kinase concentrations and the mean \pm SD of potassium concentrations at each visit and timepoint (where applicable) during each period will be graphically represented. In addition, spaghetti plots of the creatine kinase concentrations and potassium concentrations will be provided by visits and timepoints (where applicable) during each period.

Blood and urine samples for clinical laboratory tests will be collected at the times detailed in the Schedule of Activities in the protocol. At Screening (Period 1), the samples will be collected at the NIH Clinical Center. Additional testing during the Screening period or for Screening Period 2 (cohort 1 subjects) may be conducted at a local laboratory near the subject. All laboratory tests during the Treatment Periods 1 and 2 (days 1 to 5) and Weeks 8, 16 and 24 for Period 3 as well as Months 6, 12, 18 and 24 for LTE will be measured at the NIH Clinical Center. At other visits and per the schedule of events, local laboratory collection of blood and urine will be performed.

The clinical laboratory tests listed in Table 5 will be included in the safety summary tables. Creatine Kinase and Potassium will be summarized for all periods; the other parameters will be summarized for Period 3 and LTE only. Urinalysis results will be listed.

Hematology	Hemoglobin, hematocrit, complete blood count including red cell count and indices, white blood cell count, platelet count, and differential. Coagulation tests (PT, PTT, INR).
Blood Chemistry	Electrolytes (sodium, potassium, chloride), bicarbonate, glucose, blood urea nitrogen, alanine aminotransferase, aspartate aminotransferase, alkaline phosphatase, LDH, amylase, lipase, uric acid, creatine kinase, total protein, total bilirubin, 25-Hydroxy Vitamin D.

Table 5: Safety Laboratory Parameters

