13.7.4 Post-hoc Inferential Analysis

For Period 2 and Period 3, a paired t-test to test whether the mean of baseline is equal to the mean of values at each visit will be carried out for the following parameters:

- cCa,
- iPTH,
- Blood Phosphorus,
- Blood Magnesium,
- Total Calcium Excretion.

If multiple samples are planned to be collected at a visit (serial sampling), average for that visit will be derived as follow.

- **Day 1**: average of the Day 1 post-dose samples and the 15 min pre-dose sample from Day 2;
- Day 2: average of the Day 2 post-dose samples and the 15 min pre-dose sample from Day 3;
- **Day 3**: average of the Day 3 post-dose samples and the 15 min pre-dose sample from Day 4;
- **Day 4**: average of the Day 4 post-dose samples and the 15 min pre-dose sample from Day 5;
- **Day 5**: average of the Day 5 post-morning and post-evening samples;
- Week 8: average of the Week 8 pre and post-dose samples;
- Week 16: average of the Week 16 pre and post-dose samples;
- Week 24: average of the Week 24 pre and post-dose samples.

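### In Period 3, 28 of 40 scheduled blood t-tests set a local-laboratory result against an NIH baseline; urine comparisons and LTE summaries can also cross laboratories unmarked

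*SAP*

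**What the plan says.** **Who measures what.** SAP 13.6.3 gives two sets of visits to the NIH laboratory. The first is "All laboratory tests during the Treatment Periods 1 and 2 (days 1 to 5) and Weeks 8, 16 and 24 for Period 3". The second is the six-monthly LTE visits, from Month 6 to Month 24. For the rest: "At other visits and per the schedule of events, local laboratory collection of blood and urine will be performed". SAP 10.12 lists ten Period 3 analysis visits (Weeks 1, 2, 3, 4, 6, 8, 12, 16, 20 and 24) and labels only Weeks 8, 16 and 24 as NIH visits.

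**What the outpatient panel contains.** Protocol 1.3, Table C, includes "Alb, Ca, Mg, PO4, iPTH, CTX and P1NP" in the outpatient blood panel. That covers cCa (calcium and albumin), iPTH, phosphorus and magnesium.

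**Baseline.** Under SAP 10.1 the serial-chemistry baseline for Period 2 is the pre-dose sample on Period 2 Day 1, an inpatient NIH sample, and Period 3 and the LTE inherit the Period 2 baseline. For 24-hour urine the baseline is the screening value, "regardless of the laboratory analyzing the samples, local laboratories or NIH laboratory".

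**Tests.** SAP 13.7.4 specifies, for Periods 2 and 3, "a paired t-test to test whether the mean of baseline is equal to the mean of values at each visit", for cCa, iPTH, blood phosphorus, blood magnesium and total calcium excretion. SAP 13.0 sets a two-sided 5% level without multiplicity adjustment.

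**LTE.** After transfer to CALIBRATE a central laboratory is used, and under SAP 10.14 participants' results "collected in the central lab and the lab data collected in CLTX-305-201 will be analyzed in the same outputs". The LTE has summaries of levels and change from baseline, but no tests.

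**The concern.** The trial has no control arm, so any systematic difference between two laboratories' methods is counted as change from baseline. A t-test of a local result against an NIH baseline tests drug effect plus laboratory difference, and the visible SAP text does not mark, harmonise or separate the sources. iPTH is the tested analyte where this is easiest to imagine, because it is an immunoassay. At transfer to CALIBRATE the laboratory and the study phase change together, so a step in an LTE trend could be read as loss or gain of durability, which is a secondary objective. The issue is which laboratory ran the assay, not the time of day of the draw.

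**Working it through.** The plan gives no power or error figure on this point; its sample size is not based on a powered hypothesis. There is therefore nothing of its own to reproduce.

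**1. Count of Period 3 tests by laboratory** (SAP 10.12, 13.6.3 and 13.7.4; Protocol Table C)
- Visits: 10. At NIH: 3 (Weeks 8, 16, 24). Local: 10 − 3 = 7 (Weeks 1, 2, 3, 4, 6, 12, 20).
- Blood tests: 4 parameters × 10 visits = 40. Local result against NIH baseline: 4 × 7 = 28.
- Urine calcium tests: 4 visits (Weeks 8, 16, 20, 24), of which Week 20 is an outpatient collection.
- Total: 40 + 4 = 44, of which 28 + 1 = 29 (66%) use a local on-treatment result.
- LTE and central-laboratory tests: 0.

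**2. Urine baseline.** SAP 13.7.1 takes the Period 2 screening value where available, otherwise Period 1 screening. SAP 13.6.3 allows Cohort 1's Period 2 screening to be done at a local laboratory. Cohort 1 has up to 8 participants, so up to 8 could have a local baseline by this route. The documents do not say how many do.

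**3. A laboratory offset shared by all participants.** Let the offset be δ, in units of the SD of the paired difference, with no drug effect. The paired t statistic then follows a noncentral t with n − 1 degrees of freedom and noncentrality δ√n. The rejection probability is P(|T| > t at 0.975 with n − 1 df). The value n = 16 is the planned size; n = 10 is the sum of the two cohort minima, 5 + 5. The values of δ are assumed.

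| δ | δ√n at n = 16 | Rejection, n = 16 | Rejection, n = 10 |
|---|---|---|---|
| 0 | 0 | 5.0% | 5.0% |
| 0.1 | 0.4 | 6.6% | 5.9% |
| 0.2 | 0.8 | 11.6% | 8.8% |
| 0.3 | 1.2 | 20.3% | 13.6% |
| 0.5 | 2.0 | 46.5% | 29.3% |

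**4. Offsets that differ by participant.** Give the offsets mean μ and SD τ, and let σ be the SD of the paired difference without them. The noncentrality becomes μ√n / √(σ² + τ²). With μ = 0 it is zero, so the error stays near 5%, and the SD grows by √(1 + τ²/σ²). For example, τ = 0.5σ (assumed) gives √1.25 = 1.12, a loss of precision rather than false positives.

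**5. LTE mixing.** If a fraction f of participants at a visit have central-laboratory values with offset d, the visit mean moves by f × d. With assumed f = 0.5 and d = 0.2 mg/dL, that is 0.1 mg/dL.

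**The case against.** **The primary result does not depend on this.** A reader might infer that the cCa efficacy conclusion is compromised. It is not: both the Week 24 average and the Day 1 baseline are NIH values, and the window rule in SAP 10.12 keeps the NIH result at NIH visits. This stands in full.

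**Nothing from the central laboratory is tested.** A reader might also infer that local, NIH and central data are all pooled into one test. SAP 13.7.4 stops at Period 3, and Period 3 results are tabulated by visit, each scheduled at one type of laboratory. Mixing NIH or local values with central ones within a visit can arise only in the LTE. Nor does the laboratory drift steadily with time on drug: NIH and local visits alternate, and only the move to CALIBRATE is tied to time.

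**The shared-offset model may not fit.** SAP 13.6.3 describes screening-period local testing as near the subject, which suggests different laboratories for different participants. Step 4 then applies more than step 3. This stands, so the 7% to 47% range is illustrative.

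**The tests are post-hoc.** SAP 13.0 disclaims formal testing of efficacy variables, and no sample size or stopping rule rests on these p-values. This limits the weight of the point.

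**Local collection need not mean local assay.** SAP 13.6.3 speaks of local collection, and Protocol 8.3.1 puts all PD blood under the NIH laboratory. Against that, 13.6.3 contrasts local visits with those measured at NIH, and SAP 10.1 expects local laboratories to analyse some urine. Local assay is the natural reading, but the two documents need reconciling.

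**Bone markers.** CTx and P1NP are not t-tested. SAP Table 6 shows their change from baseline for Period 1 only, although the LTE endpoint list in SAP 9.0 differs.

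**Text not available.** SAP 10.13 and 10.15 were removed before review and 13.7.3 is not visible. The change history says version 3.0 clarified subject-specific handling for iPTH, so a relevant rule there cannot be excluded.

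**Conclusion.** The point holds in a limited form. Taking local collection to mean local assay, 28 of 40 scheduled Period 3 blood t-tests cross from a local laboratory to an NIH baseline. The 24-hour urine calcium comparison, part of the primary efficacy endpoint, may cross laboratories even at Week 24. LTE descriptive summaries can combine central-laboratory with NIH or local values. The primary Week 24 cCa comparison is sound on this point.

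The size of any bias is unknown. The error rates need an offset common to all participants, and both that and its size are assumptions. What the documents support is that most outpatient p-values and the LTE trend after transfer cannot be cleanly read as drug effect, and that a cheap change would remove most of the ambiguity.

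**What to change.** - **SAP 13.7.4, blood:** limit the Period 3 t-tests to Weeks 8, 16 and 24, and show the local visits descriptively, marked as local. This leaves 4 × 3 = 12 blood tests, all NIH to NIH.
- **24-hour urine calcium:** identify the laboratory of each baseline and add a sensitivity analysis restricted to participants with an NIH baseline. Show Week 20 descriptively, leaving 3 urine tests. In total 12 + 3 = 15 of 44 tests remain, including every Week 24 test.
- **SAP 10.14:** show laboratory source in LTE outputs and summarise change from baseline by laboratory, with an NIH-only summary as sensitivity. Keep the central-laboratory values: dropping them would discard post-transfer information on LTE secondary endpoints.
- **Reconcile** Protocol 8.3.1 with SAP 13.6.3 on who analyses outpatient blood, and state any handling rule for iPTH.

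A paired NIH and central-laboratory bridge at transfer is not proposed: the only aliquot the documents send to the central laboratory is for the pregnancy test.

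The cost is SAP wording and a laboratory flag on data already held. The outpatient weeks lose their post-hoc p-values, and the sensitivity subsets will be small.
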